## VIII. *Participant Compensation*

To compensate participants for their time, participants will receive cash. The payments will be allocated as follows: \$50 for completing the consent/screening and medical screening session, \$30 for the baseline visit; \$130 for completing follow-up visit 1; \$180 for completing the medication refill visit and follow-up visit 2. Participants will also receive a \$30 bonus for completing at least 75% of scheduled phone-check-ins, up to \$24 at each of the follow-up sessions (based on decisions about consuming alcohol or deferring drinks), and a final bonus of \$50 for completing all of these study components (to be paid at the final visit). Therefore, the total possible compensation is \$500 in base compensation for completing visits/questionnaires, plus up to \$48 in additional payments at the laboratory visits, for a total maximum compensation of \$548. In the event participants are not able to pick the final cash payment in person, we will offer the option of issuing the final payment via electronic gift card (e.g., Amazon) to the participant's email address.

## IX. *Project Resources*

Five private, closed door rooms are available to research staff for study visits at MRN. These assessment rooms have white noise generators outside of the doors to prevent conversations from being overheard. These are reserved by investigators as needed, and are easily accessible. All MRN research staff are trained in regards to the HIPAA Privacy Rule. All individuals will be trained to administer the same consenting and study procedures. Further, all study personnel will have current CITI and HIPAA training throughout the period of the study.

## EXPECTED RISKS/BENEFITS

---

### I. *Potential Risks*

**Safety and Side Effects Profile of Lorcaserin.** Lorcaserin (Belviq®) received FDA approval in 2012 for the indication of weight reduction in patients with obesity (or patients with overweight status and at least one weight-related comorbid condition, such as diabetes). Lorcaserin received FDA approval based on the results of three large, Phase III randomized trials totaling nearly 7,800 subjects. In these trials, lorcaserin was efficacious for weight reduction (e.g., 47.1% of lorcaserin-treated patients had body weight reduction of 5% or more at 12 months, versus 22.6% of placebo-treated participants). The extensive evaluation of lorcaserin in Phase III trials, including subsequent pooled analyses of the safety/side effect data from Phase III trials  has generated considerable data on lorcaserin's safety profile. These trials jointly comprise the largest obesity pharmacotherapy dataset in the United States to date.

In Phase III trials lasting up to one year in duration, the most commonly reported side effect/adverse event (AE) was headache (16.8% of lorcaserin participants vs. 10.1% of placebo participants). The next most common AEs were upper respiratory tract infection (13.7% lorcaserin vs. 12.3% placebo), nasopharyngitis (13.0% vs. 12.0%), dizziness (8.5% vs. 3.8%), and nausea (8.3% vs. 5.3%). Side effects were generally time-limited, with differences in side effects between experimental groups being observed primarily during the first 1-2 weeks of medication. Rates of serious adverse events (SAEs) were 2.7% and 2.3% in lorcaserin and placebo groups, with 0.3% and 0.2% of participants in these respective groups experiencing treatment-emergent SAEs. None of the reported SAEs occurred in more than one participant. Study discontinuations due to AEs were slightly more common in the medication than placebo groups, however, the placebo-adjusted discontinuation rate of medication-emergent AEs was small (1.8%). Headache was the only single AE associated with a discontinuation rate of >1% (1.8% lorcaserin, 0.8% placebo). There was no evidence of treatment-emergent psychiatric side effects (e.g., increases in depression, suicidality) or symptoms of "serotonin syndrome."  Pooled analyses from the Phase III trials also showed that lorcaserin-treated participants had significantly improved outcomes on several secondary measures relative to the placebo group, including significantly greater improvements in lipid profiles and glycemic indicators. Notably, the medication group also reported greater improvements on a measure of

quality of life . Based on Phase I research with lorcaserin, the drug received a Schedule IV designation upon its FDA approval in 2012, due to potential perceptual or quasi-hallucinogenic effects of the drug. However, in a Phase III project examining lorcaserin as an obesity treatment involving roughly 3,400 participants, no reports of hallucinogenic effects emerged in lorcaserin-treated participants, and only six participants reported mild-to-moderate euphoric effects while taking the drug . Further, subsequent experimental research has suggested no effects on perceptual outcomes, and that the drug has very low abuse potential . Acute doses of 40mg and 60mg (considerably higher than the FDA-approved twice-daily 10mg dose) were associated with higher reports of disliking the drug, again indicating unlikely abuse potential . As noted above, there were no unusual safety concerns noted in a Phase II trial of smokers . Following FDA approval in 2012, Belviq® entered the U.S. market in 2013. Since then, no new safety concerns have been noted . Overall, based on extensive Phase II and III research with obesity, and initial Phase II research in substance use disorder populations, lorcaserin is proposed as a promising treatment option for substance use disorders .

Absence of side effects associated with nonspecific serotonergic agents. Past efforts to advance non-selective serotonergic agents (e.g., *fenfluramine/phentermine*, *fen-phen*) for obesity - as well as efforts to investigate their efficacy for addiction - were halted due to adverse side effects. However, it is important to note that cardiac and psychiatric side effects of *fenfluramine/phentermine* are attributable to activation of 5-HT2B and 5-HT2A receptors. These side effects are not part of the profile of lorcaserin, which is highly selective for the 5-HT2C receptor. This finding was borne out in the Phase III obesity trials: pooled data that included 20,000 echocardiogram readings over two years of medication exposure found no evidence for increased risk of cardiac valvulopathy .

Safety profile in participants with substance use disorder. Findings from the first trial of lorcaserin for substance use disorder, which aimed to examine the efficacy and safety profile of lorcaserin in smokers, were consistent with the aforementioned findings . Smokers in this study were either normal weight or overweight, under-weight participants (<18kg/m^2) were ruled out due to a lack of safety studies in this population. The most commonly reported side effects included headache, nausea, dizziness, and constipation. Most AEs were mild or moderate, with no AEs in lorcaserin groups exceeding the rate of the placebo group by more than 3.5%. Rates of any AEs and AE-related discontinuations were 62%/2.5% and 55%/3.0% in the lorcaserin 10mg BID and placebo groups, respectively . No unique safety risks were noted in smokers relative to the results from obesity trials. Overall, neither the Phase III obesity trials (totaling nearly 7,800 participants) nor the Phase II smoking cessation trial (involving 603 smokers) reported any potential interactions or contraindications with nicotine, alcohol or other commonly used drugs. Notably, *there are now a number of randomized trials underway examining lorcaserin in participants with drug use and substance use disorder*, including trials on tobacco, cocaine, and cannabis. A full list of registered randomized trials can be found by searching for "lorcaserin" at [ClinicalTrials.gov](http://ClinicalTrials.gov). While we have no reason to expect adverse effects specific to our study population, we plan to carefully monitor participants to assess potential side effects, and will form a DSMB prior to initiating recruitment.

Monitoring will be the primary responsibility of the PIs and the study physician, who will meet weekly to discuss the status of the trial. In addition, we will establish a Data and Safety Monitoring Board to maximize safety. The DSMB will include two physicians, and the head of the IRB,. This board will meet at least every six months to review data quality, recruitment and retention, and to review all serious or clinically significant adverse events. In addition, the board will review safety data following any serious adverse event that appears to be study related. Patterns of adverse events as well as individual events may indicate the need for operational changes, protocol modifications, a decrease in dose, or, conceivably, discontinuation of the trial.

Pharmacokinetic and pharmacodynamic profile. According to the prescriber's brochure, lorcaserin reaches peak plasma concentrations in 90 - 120 minutes after oral dosing. Steady-state plasma levels are achieved after 3 days of twice-daily dosing, and the plasma half-life is roughly 11 hours.

Human studies have demonstrated that lorcaserin distributes to cerebrospinal fluid and the CNS. Lorcaserin is metabolized via multiple enzymatic pathways in the liver and excreted primarily (92%) in urine. Its metabolites shows no activity at 5-HT receptors.

*Selected dosage and medication duration.* The current study will use the FDA-approved dosage of 10mg twice- daily (BID). This dosage was used in the recent smoking cessation trial noted above. We will use a 7-day medication schedule because a) this allows more than adequate time to reach steady-state plasma levels, and b) this time frame allows us to capture short-term changes in naturalistic smoking/craving in this sample. Of note, recent data suggest that lorcaserin has acute effects on reducing nicotine intake when administered 15 min. prior to testing , suggesting that short-term medication exposure is adequate to observe effects on addiction-related outcomes. In addition, the first neuroimaging study of lorcaserin found differences in neural reactivity to hedonic food cues following one week of treatment .

**Questionnaire and Interview Assessments.** There are potential psychological risks associated with assessment procedures. Participants may find the battery of psychiatric and psychological assessments tedious or intrusive. Participants may experience discomfort resulting from questions about personal histories or substance use patterns.

**Participation in Alcohol Administration Sessions.** Other potential risks include those related to participation in alcohol administration sessions. For example, it is possible that participants may experience dizziness/nausea from drinking during these visits, or during smoking breaks. Our group has considerable experience with alcohol administration and self- administration procedures , and the safety precautions required in these studies. These procedures will follow the NIAAA recommended guidelines for administering alcohol to human subjects (<https://www.niaaa.nih.gov/Resources/ResearchResources/job22.htm>). In particular, we have taken measures to protect against ethical concerns by excluding treatment-seekers or those engaged in an active quit attempt.

**Confidentiality/Privacy.** Risks from potential breaches of confidentiality include invasion of privacy, as well as social and economic risks. Economic risks include alterations in relationships with others that are to the disadvantage of the subject, and may involve embarrassment, loss of respect of others, labeling with negative consequences, or diminishing the subject's opportunities and status in relation to others. There is also a risk of breach of data confidentiality (uncommon).

**Risks Related to DNA Collection.** The purpose of collecting saliva for DNA in this study is to allow secondary analyses to examine whether medication effects might be different according to certain genetic factors. The main aim of this analysis will be to examine the *CYP2A6* gene, which is related to nicotine metabolism. These analyses may also focus on genetic factors potentially associated with drug use or related behaviors, such as impulsivity. Potential risks associated with DNA collection involve potential identification, and there may be risks with genetic (DNA) tests that are as yet unknown. Genes may be shown at some point in the future to be related to mental illnesses or tendency to addiction. Samples will be labeled with participant ID only, and analyzed at an outside laboratory. Samples will be destroyed upon completion of the analyses. We will not conduct any whole genome sequencing of the DNA samples. Additionally, the consent form will state that participants have the option to opt out of DNA collection, and to request that their samples are destroyed at any time during the study. Participants will not receive any feedback from any of the genetic tests from study staff.

Plan for Preventing/Minimizing Risks:

*Provisions to Monitor the Data to Ensure the Safety of Subjects:*

**Medication and Side Effects Monitoring.** Although we anticipate the risk of adverse events to be low based on the safety profile of the medication, several steps will be taken to track and report medication-related side effects. A project staff member will contact participants during medication weeks to assess potential side effects. Participants will be given a contact number for study medical staff in case of serious emergent side effects. Participants will return to the lab for repeat follow-up examinations (including weight, heart rate/blood pressure measurements) following the 7-day medication phase. All adverse events will be documented and reported in accordance with UNM OIRB and MRN policies, applicable FDA regulations, and the regulations of NIH.

**Confidentiality/Privacy.** Any computerized data will be password protected and contained on a secure, password-protected computer or a secure server. Recruitment data (de-identified) will be stored in a secure, password-protected file accessible only to the study investigators and personnel. At the end of recruitment, eligible subject files will be separated from those failing to meet eligibility criteria, and records of ineligible recruitment subjects will be anonymized. Data pertaining to screening failures will be tabulated in an anonymized fashion. Data collected in other formats (e.g., medical screening notes) will be labeled only by study identifier and stored in binders in secure, locked cabinets while the study is taking place. Files will be stored and archived in accordance with Good Clinical Practice (GCP) standards. For all questionnaire and interview assessments, participants will be informed that they may decline to answer any question if they so choose.

**Risks Related to Alcohol Administration Sessions.** To ensure participant safety, a member of the study staff will be present for the duration of all alcohol administration sessions, and a member of the study medical staff will be on call during these sessions. As noted, we are recruiting participants who are non-treatment-seeking, due to the laboratory alcohol self-administration procedures. Additionally, any participants who express a desire to seek treatment during the study will be excused from further participation and provided with cessation resources. Co-I [name], an addiction psychiatrist, will provide participants with referral advice as needed.

As per the NIAAA guidelines, research studies involving alcohol administration are typically restricted to non-treatment-seeking participants in order to minimize ethical concerns, as will be the approach in this study. Regarding alcohol dose, we will use sex- and body-weight adjusted formulas to ensure that the BrAC increments associated with the alcohol session beverages approximate the intended range (increment of .03g% for the priming drink, and average increments of .015g% for subsequent drinks). BrAC levels are estimated to decline at an approximate rate of .015g% to .020g% per hour (with variability across participants), thus, BrAC levels will remain within a safe range considering the two-hour self-administration period (with 4 drinks allowed per 1-hr. block). Participants will have undergone a medical screen prior to participation, and will be excluded if the study medical staff has reason to believe that alcohol is contraindicated (e.g., due to medical conditions or medications). Vitals signs (HR, BP) will be measured during the sessions. Following the completion of alcohol sessions, participants will be escorted to a private room designated for recovery purposes. Participants will only be discharged after their breath alcohol concentration is <.03g% (verified by at least two separate readings), consistent with NIAAA recommendations. Participants will also be provided with reimbursement for transportation if they have not arranged for a ride (participants will be instructed not to drive to the session).

**Compensation for Research-Related Injury.** No commitment is made by MRN to provide free medical care or money for injuries to participants in this study. This is clearly stated in the consent form.

**Economic Burden to Subjects.** Participants will not be charged for any of the experimental study procedures. If incidental findings from the study (e.g. abnormal EKG findings or abnormal hepatic/metabolic labs) result in the need for further evaluation/treatment, the participant or their insurance company will be responsible for additional clinical evaluation/treatment that may be

needed. Also, incidental finding information is disclosed only to the individual participant. However, if a participant chooses to disclose such information to their personal physician, this may become part of their medical record which may or may not have an effect in the future on getting health or life insurance.

## II. *Benefits*

The participants in this study are not expected to benefit directly from their participation. However, the knowledge gained from this study could lead to a better understanding of a medication with potential to treat AUD, and potentially other substance use disorders. Given the use of an FDA-approved medication that has been deemed safe in the context of chronic administration for weight reduction, the risks to which participants will be exposed during this short medication screening trial are deemed relatively small in comparison to the potential benefits of the proposed research (i.e., demonstrating potential efficacy of a new medication).

## III. *Privacy of Participants*

Five private, closed door rooms are available at MRN. The rooms have white noise generators outside the doors to prevent conversations from being overheard. All staff are trained in the HIPAA Privacy Rule.

## IV. *Unanticipated Problems/Adverse Events*

All project staff will be trained to identify adverse events (AEs), which must be reported to the PI within 24 hours, and serious adverse events (SAE) must be reported to the PI as soon as possible after a staff member becomes aware of an SAE. In addition, any unanticipated participant issues will be discussed in weekly staff meetings, which will provide another opportunity to identify AEs. Anticipated problems and AEs will be reported to the OIRB within 7 calendar days.

## PROJECT DATA

---

### I. *Data Management Procedures and Confidentiality*

**Consent Forms:** Signed consent forms are stored in a locked cabinet in a locked office at MRN.

**Questionnaire Data:** All data are coded with a unique research subject identifier (URSI) number. Electronic data are stored on a drive only accessible by the research team on a secure MRN server and/or in the COINS database on a secure HIPAA compliant cloud based server. Electronic data captured by RedCap are stored on a secure server, and identified by participants ID only. For non-computer based forms, such as the neuropsychological assessments, the data collection sheets are stored in a locked cabinet in a separate locked data storage space at MRN.

**Behavioral Data:** All data are coded with the URSI, and collected and stored electronically. Electronic data is stored on a drive only accessible by the research team on a secure MRN server. De-identified data resulting from this study may also be presented at meetings, published in journals/books, used in classrooms for training/teaching purposes, and may be shared with other

researchers including scientists at other universities and institutions. In addition, this study will be registered at ClinicalTrials.gov, and de-identified information from this study will be submitted to ClinicalTrials.gov.

*Data and safety monitoring plan:* See attached plan.

*Certificate of Confidentiality:* In addition to the above protections, this study has a Certificate of Confidentiality from NIH to further protect participant confidentiality. Importantly, as stated in the consent, participants are informed that if they report current abuse of a child or an elder, we will report the person to the proper authorities, consistent with New Mexico state law.

Finally, participants will be given the option of having all their data (behavioral assessments) stored in the MRN Data Repository (UNM HRRC# 06-387, PI: [name]).

## II. *Data Analysis/Statistical Considerations*

Primary and secondary outcomes will be evaluated using mixed linear effects models with condition (lorcaserin, placebo) as a within-subjects factor and medication order as a between-subjects factor. Maximum likelihood estimation will be used to account for missing data by analyzing all available cases. The primary outcome is number of laboratory drinks consumed. Using the same model, the secondary outcomes examined will be (1) cigarette and alcohol demand (based on corresponding purchase tasks) and self-reported craving after the priming alcohol dose, (2) levels of alcohol effects (stimulation/sedation) after the priming alcohol dose, and (3) cigarettes per day and drinking frequency/quantity during the 7-day medication phase. Exploratory analyses will also examine changes in alcohol stimulation/sedation and alcohol/cigarette demand and craving across all assessment time points (i.e., 30/60/90/120 minutes) by including time as an additional within-subjects factor and BrAC as a time-varying covariate. Mixed linear effects models will be adapted to examine medication effects on impulsivity/learning tasks constructs, and medication tolerability and side effect profiles. Sex will be examined as an exploratory moderator in all analyses.

*Statistical Power.* Because no human data on lorcaserin's effects on laboratory alcohol outcomes are available, we examined medication effect sizes in prior studies using similar populations involving the laboratory tasks that serve as our primary outcome (alcohol self-administration) and key secondary outcomes (subjective response to a moderate dose of alcohol). In studies of heavy-drinking smokers, varenicline yielded a large effect on number of laboratory drinks consumed (Cohen's  $d = 0.97$ ;  $N = 10$  per group, between-subjects) and small-to-large effects on subjective alcohol effects at doses of .03g% or .06g% ( $d \sim 1.00$ ;  $d = 0.18$  to  $0.93$ ;  $N = 30$  per group, between-subjects). Taking into account the potential for a smaller effect size for lorcaserin relative to varenicline, power analyses assumed a medium effect size. We selected a within-subjects design, which is recommended to maximize power in medication screening studies, and assumed a within-subjects correlation of 0.60 for laboratory outcomes (as reported in prior cross-over human laboratory medication screening designs). Using these assumptions and an alpha of .05, we estimated power in G\*Power software using a fixed effects, within-subjects design and two time-points. Conservatively, a final sample of  $N = 34$  allows sufficient power (.80) to detect a medium within-persons medication effect on primary and secondary outcomes. To allow for roughly 20% attrition during the medication trial, we propose to randomize 42 participants to arrive at the final sample.

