### I. *Target Population and Inclusion/Exclusion Criteria*

A final sample of 42 smokers with AUD (balanced by sex) will be recruited from the community.

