## II. *Participant Enrollment*

We anticipate phone screening up to 1000 individuals and may enroll up to 100 participants in order to obtain a final sample of 42 eligible participants who complete all study visits.

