*Impulsivity/Learning Tasks:* To examine medication effects on behavioral measures of impulsivity and reward-based learning (as reported in preclinical studies), participants will complete computerized cognitive tests of impulsive action, attention, and reward-based learning at the baseline session, lasting roughly 45 minutes in total duration. These measures will be repeated at follow-up visits. Additionally, any measures noted above that would be expected to show change across sessions (or in response to medication) will be repeated at follow-up visits 1 and 2. These measures include: Stop Signal task, CPT, Reward Responsiveness Test, Monetary Choice Questionnaire, Food Discounting Task, Alcohol Purchase Task, and Cigarette Purchase Task.

The baseline session is projected to take approximately 2-3 hours. Patients will be given breaks, snacks, and bottled water as needed.

**Medication Schedule and Safety Monitoring.** Participants will receive the first 7-day supply of pills (medication or placebo, randomized and counterbalanced) at the completion of the baseline visit. In the first Phase II trial of lorcaserin for smoking cessation, the FDA-approved dose of 10mg BID (twice-daily) significantly increased abstinence relative to placebo, with a larger effect size relative to a comparison low-dose condition (10mg QD / once-daily) . The BID and QD conditions were equivalent on discontinuations due to adverse events (AE; 2.5% and 3.0%, respectively) . Therefore, we will use the FDA-approved dose of 10mg BID. Of note, steady-state plasma concentration occurs in 3 days. All pills will include a small amount of riboflavin to facilitate urinalysis as an index of adherence, and participants will be asked to bring their pill bottles at each visit. To monitor emergent side effects, the study staff will contact participants twice during the 7 day period (e.g., days 2 and 4). Participants will complete a brief web-based assessment each morning using Redcap (link texted by research staff or automated system), including 1) prior-day number drinks consumed; 2) number of cigarettes smoked; 3) side effects; and 4) medication

adherence for the prior day. Participants will be texted a link to the survey, which can be completed via smartphone. If preferred, participants can opt to receive an email link, or a text message with these questions embedded in a SMS text.

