On Day 7 participants will return to complete the alcohol administration session described below. This visit will also include a repeat medical screen/measurements (as noted above), a calendar-based assessment of interim alcohol use and cigarette use, and a pill count. Following the laboratory visit on Day 7, participants will undergo a 7-day washout phase. Next, they will repeat the same 7-day sequence in the alternate pill condition, culminating in a second, identical alcohol administration session. Depending on scheduling and participant availability, we will be flexible in accommodating slight deviations from the 7-day schedules noted above, and at the discretion of the study physician, participants may be provided with additional days of medication as needed.

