*Alcohol self-administration protocol.* Medication effects on alcohol intake will be examined using a validated oral self-administration procedure, which has been established as sensitive to medication effects. After completing physiological readings (systolic and diastolic blood pressure, heart rate) and baseline measurements of self-report questionnaires (e.g., measures of alcohol and cigarette craving and demand, see Measures), the procedure will commence with a scheduled *priming drink*, calculated to achieve a target breath alcohol concentration (BrAC) of .03g%. The priming drink serves two purposes: 1) to allow investigation of within-subjects medications effects on self-report outcomes (e.g., subjective effects, craving) following a controlled, low dose, and 2) to serve as a prime for the subsequent self-administration period. The priming drink will include 1 part 80-proof liquor (of the participant's choice) to 5 parts mixer, and will be consumed as a bolus dose over 5-10 minutes, followed by an absorption period lasting approximately 30 minutes. At the completion of the priming phase, participants will complete the next set of self-report measures, including alcohol and cigarette craving, alcohol and cigarette demand, and subjective effects of alcohol, (see Measures).

After the post-priming assessments, participants will complete a 2-hour *ad libitum* self-administration period, separated into two 1-hour blocks. Participants will be allowed to self-administer up to 8 additional "mini-drink" beverages (4 per block), each calculated to achieve an average BrAC increment of .015g% per drink. Prior research with this protocol shows that participants tend to show modest levels of alcohol ingestion (averaging 30-40g, equivalent to 2-3 standard drinks), on average. This finding is consistent across studies of both non-dependent

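### The crossover model names condition and medication order but no period term, so as written a shift between sessions 1 and 2 stays in the error variance and costs power

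*Combined protocol and SAP*

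**What the plan says.** The section on data analysis and statistical considerations gives one model for all primary and secondary outcomes: "mixed linear effects models with condition (lorcaserin, placebo) as a within-subjects factor and medication order as a between-subjects factor". For missing data it adds: "Maximum likelihood estimation will be used to account for missing data by analyzing all available cases". The only time factor in that section is assessment time within a session, and it belongs to exploratory analyses. The only moderator named is sex. No section names a period, session or visit term, or a condition-by-order interaction.

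The design is a two-period crossover. The first week's pills are "medication or placebo, randomized and counterbalanced". After a 7-day washout the other condition follows, "culminating in a second, identical alcohol administration session". The primary outcome is a count of drinks taken in the laboratory: "Participants will be allowed to self-administer up to 8 additional" small drinks after the priming drink.

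The power paragraph "assumed a within-subjects correlation of 0.60 for laboratory outcomes", takes a medium effect and alpha .05, and arrives at 34 analysed participants for power .80. It randomizes 42 to allow for about 20% attrition. Two other sections treat 42 as the completed sample: "A final sample of 42 smokers with AUD (balanced by sex) will be recruited from the community", and enrolment continues "in order to obtain a final sample of 42 eligible participants who complete all study visits". Both counts are therefore used below.

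**The concern.** Each participant has one order, so the order main effect compares two groups of people. It explains nothing in the within-person difference between lorcaserin and placebo. A shift from the first to the second session enters that difference with opposite signs in the two orders. Counterbalancing makes the shift cancel in the mean when completers are balanced, but it does not remove it from the spread of the differences.

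The wording allows two readings:

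- **(a) Main effects only.** The shift inflates the standard error and lowers power. With unequal completers it also biases the estimate.
- **(b) A full factorial including condition by order.** The interaction absorbs the shift and the power loss disappears.

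Two analysts following the text could therefore report different standard errors for the primary test. A shift is plausible because participants meet the same drink-or-money choice a second time, and the plan itself expects some repeated measures to change across sessions.

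**Working it through.** **Inputs.** From the plan: correlation r = .60, alpha .05, 34 analysed, 42 randomized (or 42 completers). Assumed: a medium effect means d = 0.5; tests are two-sided; the session shift δ is 0.25, 0.5 or 0.75 outcome SD, because the documents give none.

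**1. The plan's own figure.** The SD of a within-person difference is √(2(1−r)).

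- r = .60: SD = √0.8 = 0.894, so dz = 0.5/0.894 = 0.559. Power .80 needs N = 28; N = 34 gives 0.886.
- r = .50: SD = 1.0, so dz = 0.5. Power .80 needs N = 34 (power 0.808).

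The stated N of 34 is thus reproduced at r = .50, not at .60. The plan calls its N conservative, so the mismatch is in the safe direction. It does mean that both correlations should be shown. Attrition: 42 × 0.8 = 33.6, or about 34.

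**2. Effect of omitting period.** With balanced orders the true variance of the mean difference remains 2(1−r)/N, but the model estimates about (2(1−r) + δ²)/N. At r = .60 and N = 34 the reported standard error is about √(0.8/34) = 0.153 at no shift and √(1.05/34) = 0.176 at δ = 0.5.

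Power was simulated with 400,000 replicates per scenario. Period omitted is a one-sample t test on differences (N−1 df). Period included is the mean of the two order means with pooled variance (N−2 df).

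| Completers, r | No shift | 0.25 SD | 0.5 SD | 0.75 SD | With period term |
|---|---|---|---|---|---|
| 34, .60 | 0.89 | 0.87 | 0.82 | 0.72 | 0.88–0.89 |
| 34, .50 | 0.81 | 0.79 | 0.74 | 0.64 | 0.81 |
| 42, .60 | 0.94 | 0.93 | 0.90 | 0.83 | 0.94 |
| 42, .50 | 0.89 | 0.87 | 0.83 | 0.76 | 0.89 |

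Type I error with period omitted falls to 4.2–4.4%, 2.5–2.9% and 1.1–1.5% at the three shifts; with period it is 5.0%.

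**3. Equivalence of the two remedies.** In one simulated data set (34 participants, δ = 0.5), a mixed model gave a standard error for condition of 0.173 with condition and order. It gave 0.152 both when period was added and when condition by order was added instead.

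**4. Bounded count.** The outcome runs from 0 to 8. Repeating step 2 with a rounded, clipped outcome (34 completers, observed r = .60) gave:

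- mean 4.0, SD 2.1: 0.89, then 0.87, 0.82, 0.71 (with period 0.88–0.89);
- mean 2.5 with 26% zeros: 0.89, then 0.87, 0.80, 0.68 (with period 0.85–0.89).

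The Gaussian figures hold to within about 4 points.

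**5. Unequal completers.** Using complete pairs only, the fraction of the shift that enters the estimate is (n₁−n₂)/N. If all 8 dropouts supply session 1, generalized least squares at r = .60 gives a smaller fraction. The last column is hypergeometric: 8 dropouts from 21/21, unrelated to order.

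| Split | No dropout supplies session 1 | All do | Bias at δ = 0.5 | Chance of a split at least this unequal |
|---|---|---|---|---|
| 19/15 | 4/34 = 12% | 10% | 0.05–0.06 SD | 24% |
| 20/14 | 6/34 = 18% | 15% | 0.07–0.09 SD | 4.5% |
| 21/13 | 8/34 = 24% | 20% | 0.10–0.12 SD | 0.3% |

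The sign depends on which order loses more people. When the bias is towards zero, a 20/14 split of complete pairs at δ = 0.5 and r = .60 gives an estimate of 0.50 − 0.176 × 0.5 = 0.41 and power .64, against .87 with a period term.

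**The case against.** The plan speaks of within- and between-subjects factors, which is factorial language, and such designs are often fitted with the interaction. An order main effect alone does little for the condition contrast, so the interaction may be why order is there. This stands as a plausible reading; the point is then under-specification rather than a proven error. The text still does not settle it. With reference coding, the condition coefficient in a factorial fit would also apply to one order only.

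On the plan's stated r = .60 with 34 completers, power stays at or above .80 until the shift reaches about 0.55 SD; with 42 completers, about 0.8 SD. That is correct. Results below .80 at small shifts need r = .50, which the plan does not state but which reproduces its N. The shift is wholly assumed, and nothing in the documents supports the upper end of the range.

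Under balance the estimate is unbiased and the test conservative, so false positives do not increase. Bias needs both a sizeable shift and unequal completion, and the more unequal splits are unlikely if dropout is unrelated to order. All of this stands. It limits the size of the problem without giving a reason to leave the term out.

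**Conclusion.** The concern holds. The model as written omits period, and the order term does not replace it. Under the main-effects reading with balanced orders, the loss is about 1–2 points of power at a 0.25 SD shift, 4–7 at 0.5 SD and 11–17 at 0.75 SD. Whether power drops below .80 depends on the correlation and on which completer count applies. Unequal completion adds a bias of roughly 10–24% of the shift for splits from 19/15 to 21/13.

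These sizes rest on d = 0.5, an assumed shift range and the main-effects reading. Under the factorial reading only a clarification is needed. This should be changed, as an inexpensive improvement to the primary analysis; it does not make the trial invalid. Confidence is moderate because the intended model is not clear from the text.

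**What to change.** For the primary and secondary outcomes, and for the impulsivity and tolerability models, state: fixed effects for condition, period (first or second medication phase and its session) and medication order, with a random participant intercept. If the condition-by-order interaction was intended, name it, say that it is the period effect, and use sum-to-zero coding so that the condition term averages over both orders. Report completers by order.

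The cost is one sentence and one degree of freedom. With balanced orders and no shift, power at 34 completers and r = .60 is 0.885 with the term against 0.886 without. With unequal completers and no shift, it costs about 0.5 points at 19/15 and 2 points at 21/13.

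A separate, minor addition is to use REML with a small-sample degrees-of-freedom method, which still uses all available cases. The plan names no test. If maximum likelihood were paired with a Wald z test, type I error at N = 34 and no shift would be about 6.2–6.6%. At a 0.5 SD shift with period omitted it would be 3.3–3.7%, so the two effects partly offset.
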